4.3 Duration of Trial by Phase

Time expected for all participants to be enrolled:	5 years
Duration of individual participant participation:	90 days during the treatment phase 90 days during the follow up phase 180 days total participation
Total duration of trial (excluding data collection and analysis):	5 years

5. PARTICIPANT SELECTION

5.1 Participant Population

The study population will be comprised of men and women of all races, ethnic groups and socioeconomic status of the ages of 21 and greater admitted to the hospital with a clinical diagnosis of AH. The definition of AH is based on criteria established by NIAAA. A conscious decision not to require a liver biopsy for inclusion was made based on the current low rate of liver biopsy used to establish this diagnosis in the US and the ability to diagnose the condition with relative accuracy based on the experience in the first cycle of funding. Eligible participants will be identified based on inclusion/exclusion criteria as defined below.

Inclusion Criteria/ Exclusion Criteria

Inclusion Criteria

1. AH, as defined by the NIAAA pan-consortia for AH:
 - a) Onset of jaundice (*defined as serum total bilirubin >3 mg/dL*) within the prior 8 weeks
 - b) Regular consumption of alcohol with an intake of > 40 gm daily or >280gm weekly on average for women and > 60 gm daily or >420gm weekly on average for men for 6 months or more, with less than 8 weeks of abstinence before onset of jaundice
 - c) AST > 50 IU/l
 - d) AST: ALT > 1.5 and both values < 400 IU/l
 - e) and/or histological evidence of AH*
2. MELD 20-35 on day of randomization.
3. Ages ≥ 21

**In patients with possible AH or AH with confounding factors such as possible ischemic hepatitis, possible DILI, uncertain history of alcohol use (e.g., patient denies excessive alcohol use), and atypical/abnormal laboratory tests (e.g., AST < 50 IU/IU/L or > 400 IU/IU/L, AST/ALT ratio < 1.5), antinuclear antibody > 1:160 or SMA > 1:80, standard of care liver biopsy may be performed during current hospital admission to confirm AH and exclude competing etiologies¹⁷.*

Exclusion Criteria

1. MELD SCORE <20 or > 35
2. Active sepsis (positive blood or ascitic cultures) with Systemic Inflammatory Response Syndrome (SIRS) or hemodynamic compromise requiring intravenous pressors to maintain tissue perfusion
3. Pneumonia as evidenced by radiological exam
4. Multi-organ failure
5. Renal failure defined by GFR <35 mL/min by CKD EPI.
6. Clinically active C. diff infection
7. History of imaging of the liver (ultrasound, computerized tomography, or magnetic resonance) showing other causes of jaundice
8. History of other liver diseases including hepatitis B (positive HBsAg or HBV DNA), hepatitis C (positive HCV RNA), autoimmune hepatitis, Wilson disease, genetic hemochromatosis, alpha1-antitrypsin deficiency, or strong suspicion of Drug Induced Liver Injury (DILI). Previously treated hepatitis C that was cured (sustained virological response with negative RNA \geq 24 weeks following treatment) is not an exclusion.
9. History of HIV infection (positive HIV RNA or on treatment for HIV infection)
10. History or presence of cancer (including hepatocellular carcinoma) other than non-melanoma skin cancer
11. History of other significant medical problems such as autoimmune diseases, severe asthma, psoriasis, Inflammatory Bowel Disease (IBD), etc. that might require immunosuppressive treatments
12. Pregnancy or breastfeeding
13. Prior exposure to experimental therapies in last 3 months
14. Prior exposure to systemic corticosteroid (glucocorticoid) or immunosuppressive therapy for more than 4 days within previous 30 days
15. Need for inotropic pressor support to maintain perfusion to critical organs within prior 48 hours before randomization and initiation of experimental treatment
16. Clinically significant pancreatitis- abdominal pain, elevated lipase ($> 3 \times$ ULN) and at least edema of pancreas with fat-stranding on CT scan
17. Total WBC count $> 30,000/\text{mm}^3$
18. Known allergy or intolerance to therapeutic agents to be tested
19. Inability to voluntarily obtain informed consent from participant or guardian
20. Perceived inability to follow study procedures and comply with protocol
21. Platelet count $< 40,000 \text{ k/cumm.}$
22. Positive PCR test for COVID -19 within 7 days prior to the baseline day 0 visit*
23. Active gastrointestinal bleeding defined as hematemesis or melena with a decrease in hemoglobin more than 2 g/dl in 24 hrs. Due to gastrointestinal bleeding, or with a decrease in mean arterial BP to $< 65 \text{ mmHg}$.

**Positive PCR test for COVID-19 is exclusionary only during screening period. If a patient tests positive any time after baseline randomization, a positive PCR test for COVID-19 will be considered as a SAE.*

The participants for this study will be recruited from a hospitalized population of participants meeting the eligibility criteria outlined above who live within one day travel from one of the

participating clinical centers and who have provided informed consent to participate in this clinical trial and who are willing to continue their participation for the anticipated follow-up period of the trial. Although the primary endpoint is survival at 90 days, follow-up visits will be continued up to 6 months.

5.2 Participant Compensation and Recruitment

5.3.1 Participant Compensation

Participant compensation is site specific.

5.3.2 Participant Recruitment

Sources of participants:

Identification of participants with severe AH requires collaboration with those physicians who manage these participants within the hospital and the emergency department. Almost 100% of participants are admitted to hospital based on the severity of their liver disease. Occasionally participants are seen in free-standing urgent care centers, free-standing emergency rooms or in office/clinic practices. Since the standard of care is to admit these participants for further evaluation to exclude infections as a precipitating cause of decompensated liver disease, most will ultimately be identified in a hospital setting. Letters will also be sent to referring MDs and referring hospitals.

Some sites in the current U01 have found that screening laboratory results for elevated AST and total bilirubin is a useful way to identify potential participants. In accordance with Institutional Review Board Policies, once identified the primary team caring for these participants must be contacted by the investigators and agree to ask the participant about their interest in participating in a clinical trial as part of the treatment of the underlying AH. Once the participant expresses willingness to be contacted the investigators may discuss details of the study and obtain informed consent prior to beginning treatment.

5.4.1 Individual Drug Discontinuation Criteria Reasons for Mandatory Trial Hold – Infection

If one of the following criteria is met, the study drugs **should be held for 3 days**:

1. Documented Infection

- Pneumonia defined as new infiltrate by CXR or chest CT scan
- Positive cultures (blood, ascites) for bacteria or fungus
- Positive fungal cultures in urine ($> 50,000$ colonies/ml)
- CNS infection defined as positive cultures or WBC > 5 in CSF
- Severe soft tissue or bone infections including clinical diagnosis of cellulitis

2. SIRS (defined as two or more abnormalities in temperature, increased heart rate, respiration, or white blood cell count) with increase in SOFA score ≥ 2 points

Participants will be reassessed on the third day of the study drugs hold: If infection clears and participant stabilizes, study drugs will be resumed.

For participants with documented infection: If infection is responsive to antibiotics and participant is stabilized or improved, study drugs may be resumed at the discretion of the clinical care team. If there is no improvement after 3 days, study drugs will be stopped

For participants meeting only SOFA+SIRS (#2 above) criteria for stopping: if cultures of urine, blood, ascites, stool (including C. diff) are negative and CXR is unchanged, study drugs may be resumed at the discretion of the clinical care team.

If the participant has a second hold of study drugs due to infection/SIRS+SOFA criteria, study drugs will be stopped.

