10.2.2 Serious Adverse Events (SAE) Classifications Common in Severe AH

Acute kidney injury:

- Increase in creatinine of 50% above baseline over a period of 7 days
- Increase in creatinine of 0.3 mg/dl within a period of 48 hrs.
- Onset of renal failure requiring dialysis

Sepsis:

- Life-threatening organ dysfunction caused by a dysregulated host response to infection
- An increase in SOFA score of 2 points or more
- Note: most participants with severe AH have 4 points based on bilirubin only

Infection:

- Pneumonia defined as new infiltrate by CXR or Chest CT scan not explained by “fluid overload”
- Positive blood cultures for bacteria or fungus, not suspected as contaminant
- Positive urine fungal culture > 50,000 colonies/ml
- Positive urine bacterial culture > 100,000 colonies/ml (mixed flora is excluded)
- Soft tissue or bone infections including cellulitis or abscess documented by exam or scan
- CNS infection defined as positive culture of CSF or > 5 WBC/ml
- Ascitic fluid white cell count > 500/ml or neutrophils > 250/ml. with or without positive bacterial or fungal cultures

Decompensation of liver disease:

- New onset of ascites if not present on admission to study
- New onset of variceal hemorrhage
- New onset of hepatic encephalopathy (HE).

Hepatic failure defined as increase in MELD score ≥ 5 on two consecutive occasions

Cerebral failure defined as worsening HE \geq Grade 3 if hepatic encephalopathy present on admission

Renal failure defined as serum creatinine ≥ 3 milligrams per liter or requirement for renal replacement therapy despite adequate volume replacement

Respiratory failure defined as need for BIPAP therapy or ventilation

Circulatory failure defined as shock or requirement of vasopressor support to maintain mean arterial pressure ≥ 60 mm Hg despite adequate volume replacement

Multiple organ failure defined as failure ≥ 2 organs

Note: Sepsis will often be an SAE that precedes documented infection by 1-5 days. If sepsis is reported as an SAE and infection is never documented, then it should be classified separately, i.e., sepsis with documented infection or sepsis without documented infection.

Sepsis can be diagnosed by minor changes in lab parameters such as decrease in platelet count from 160,000 to 90,000 or increase in creatinine to 1.3 and drop in platelet count to 100-150,000 from normal on admission. However, these changes may also occur due to worsening liver disease without infection as a cause.

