We will monitor safety closely, including all SAEs, AKI, and infection. We will provide unblinded data on SAEs including infections and AKI to the DSMB on monthly basis and hold the first DSMB after 3 months from the start of enrollment. We also propose a risk-based monitoring (RBM) approach which will create a more efficient and timely monitoring of accumulating data on the adverse events of interest, namely AKI and infections. The FDA has issued a final guidance in 2013 (Guidance for Industry. Oversight of Clinical Investigations — A Risk-Based Approach to Monitoring. August 2013) with a follow-up draft guidance in March 2019 (A Risk-Based Approach to Monitoring of Clinical Investigations. Questions and Answers. Guidance for Industry) that indicated the acceptability of RBM in studies with FDA oversight. While the details and implementation are left to the trial investigators, the overall concepts are included in these two documents – and in the Transcelerate RBM Position Paper (available at <https://www.transceleratebiopharmainc.com/wp-content/uploads/2013/10/TransCelarate-RBM-Position-Paper-FINAL-30MAY2013.pdf>). The essential elements of the study-specific AE/SAE monitoring plan would be for the RBM tools to interface with the main REDCap database so that any new AEs or SAEs would be immediately passed to the data driven RBM tools to determine if a trigger threshold has been reached. This interaction between receipt of data by REDCap and the comparison of the data to the triggers (and reporting of it on study dashboards) by the RBM tools will be virtually instantaneous. In addition, levels of thresholds can be set so that data trends of SAEs accumulating within treatment groups can be identified before significance is reached. **A complete monitoring plan, including RBM details, will be developed for review by the FDA and the DSMB within three months of study initiation.** We will also include Statistical Process Control (SPC) techniques in the monitoring plan to ensure that appropriate statistical controls are also utilized during the study.

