10.3 SAEs that are Anticipated to Occur in the Study Population (Expected SAEs)

Certain SAEs are anticipated to occur in this study population at some frequency independent of

drug exposure. Examples of these expected SAEs include variceal bleeding, ascites, spontaneous bacterial peritonitis, jaundice, hepatorenal syndrome, or hepatic encephalopathy. These expected SAEs as well as any related hospitalization will not be expeditiously reported as IND safety reports but will be reported in the manner described above (Table 4.). However, if an aggregate analysis indicates that these events are occurring more frequently in the drug treatment group than in a concurrent or historical control group, the SAEs will be reported as an IND safety report (21 CFR 312.32(c)(1)(c)). Follow up of AEs

All AEs, including clinically significant laboratory values or physical examination findings relative to pretreatment assessments, must be followed during the trial until the AE resolves, is no longer of clinical concern, has stabilized or is otherwise explained, or the participant is lost to follow up.

AEs ongoing at the final visit that are deemed to be ‘possibly, probably, or definitely’ related or of other clinical significance must be followed for as long as necessary to adequately evaluate the safety of the participant or until the event stabilizes, resolves, or is no longer of clinical concern. If resolved, a resolution date for the AE should be documented on the CRF. The investigator must ensure that follow up includes any supplemental investigations indicated to elucidate the nature and/or causality of the AE. This may include additional laboratory tests or investigations, or consultation with other healthcare professionals, as considered clinically appropriate by the investigator.

Note: Some SAEs like AKI, GI bleeding, infections, etc. can be both expected and common

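### The mandatory infection hold recognises ascitic infection only by positive culture, so culture-negative peritonitis does not by itself hold study drug

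*Combined protocol and SAP*

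**What the plan says.** Section 5.4.1 requires study drugs to be held for 3 days if any one listed criterion is met. Section 6.6.1 repeats the list for Day 0 to Day 30. The first criterion is documented infection, and its only entry for ascites is "Positive cultures (blood, ascites) for bacteria or fungus". Other entries in that list do not need a culture: a new infiltrate on chest imaging, "CNS infection defined as positive cultures or WBC > 5 in CSF", and "Severe soft tissue or bone infections including clinical diagnosis of cellulitis". The second criterion is SIRS together with a SOFA increase of at least 2 points.

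The restart rules differ by route. After documented infection, drug may be resumed at the care team's discretion "If infection is responsive to antibiotics and participant is stabilized or improved"; without improvement after 3 days it is stopped. After a hold for SIRS plus SOFA alone, negative cultures (ascites included) and an unchanged chest X-ray are enough for discretionary restart. A second hold on either ground stops study drugs.

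Section 10.2.2, which classifies serious adverse events, lists under infection: "Ascitic fluid white cell count > 500/ml or neutrophils > 250/ml. with or without positive bacterial or fungal cultures". Its CNS entry is "CNS infection defined as positive culture of CSF or > 5 WBC/ml".

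**The concern.** The protocol holds two working definitions of ascitic infection. The one that controls dosing is silent on the cell count that the other relies on, and no reason is given. A participant can therefore have an infection SAE by Section 10.2.2 and meet no hold criterion.

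This is not a remote complication. Section 10.3 says: "Examples of these expected SAEs include variceal bleeding, ascites, spontaneous bacterial peritonitis, jaundice, hepatorenal syndrome, or hepatic encephalopathy". Section 2.2.1 associates prednisone with more severe bacterial and fungal infections, Section 2.2.2 says steroids are poorly tolerated in systemic infection, and Section 2.3 lists serious infection as frequent (over 20%) with prednisone and occasional (2 to 20%) with anakinra. At stake is continued blinded dosing with either agent during an infection that the protocol itself recognises.

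**Working it through.** The documents give no figure for this point that could be reproduced, so the check is a comparison of rules followed by dose arithmetic.

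**Step 1. The two lists side by side.**

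| Site | Hold list (5.4.1, 6.6.1) | SAE infection list (10.2.2) |
|---|---|---|
| Lung | New infiltrate on imaging | Same, unless explained by fluid overload |
| Blood | Positive culture | Positive culture, suspected contaminants excluded |
| Ascites | Positive culture only | Cell count above threshold, culture positive or negative |
| Urine | Fungal culture above 50,000/ml | Same, plus bacterial culture above 100,000/ml |
| CSF | Positive culture or cell count | Positive culture or cell count |
| Soft tissue, bone | Severe infection, including clinical cellulitis | Cellulitis or abscess by examination or scan |

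The hold list is not culture-only as a policy. The CSF cell count appears in both lists; the ascitic cell count appears in only one.

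**Step 2. Apply the rules to a participant with a raised ascitic count and negative cultures.**

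- No SIRS plus SOFA rise: infection SAE under 10.2.2, no criterion met in 5.4.1 or 6.6.1, no mandatory hold.
- SIRS plus SOFA rise of at least 2: held under the second criterion. On the third day, negative cultures and an unchanged chest X-ray permit restart. The ascitic count plays no part in that decision.
- Cell count added to the documented-infection list: held under the first criterion in both situations. The participant no longer meets SIRS plus SOFA alone, so the documented-infection restart rule applies.

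**Step 3. Doses involved.** Inputs: anakinra 100 mg or placebo daily on Days 1-14, prednisone 40 mg or placebo on Days 1-30, zinc or placebo on Days 1-90.

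If a hold ends in restart after 3 days, and held doses are not made up (an assumption; the protocol does not say), the loss is at most:

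- 3/14 = 21.4% of injections
- 3/30 = 10.0% of prednisone or placebo doses
- 3/90 = 3.3% of zinc or placebo doses

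That is not the upper limit, because no improvement after 3 days means a permanent stop. If the first withheld dose is on day d of a course of length L, the doses remaining are L − d + 1. For d = 2:

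- injections: 14 − 2 + 1 = 13 of 14
- prednisone or placebo: 30 − 2 + 1 = 29 of 30
- zinc or placebo: 90 − 2 + 1 = 89 of 90

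The same applies to exposure without a hold. Three further days mean 3 × 40 = 120 mg prednisone in one arm or 3 × 100 = 300 mg anakinra in the other. Without a hold there is also no third-day reassessment and no stop for lack of improvement. From Day 2 the ceilings are then 29 × 40 = 1160 mg prednisone and 13 × 100 = 1300 mg anakinra. These are limits set by the schedule, not expected values. The Lille stop at Day 7, or any other stopping rule, would lower them.

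**Step 4. Unit of the threshold.** Section 10.2.2 prints the ascitic and CSF counts per ml, whereas blood white cells are given per mm³ (Section 5.1 exclusion 17, Section 5.4.2 item 3, Section 6.6.2.1). Since 1 ml = 1000 mm³, the ascitic thresholds read literally are 500/1000 = 0.5 and 250/1000 = 0.25 cells per mm³. If per mm³ was intended (an assumption), the true thresholds are 1000 times higher.

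**The case against.** The lists serve different purposes. Section 10.2.2 classifies SAEs and does not claim to govern dosing, and the lists differ in both directions elsewhere (bacterial urine culture, contaminants, fluid-overload infiltrates). Exclusion criterion 2 in Section 5.1 also uses positive blood or ascitic cultures, which could suggest a consistent culture-based standard. These points stand to this extent: the lists need not match line by line, and the other differences are not faulted here. They do not explain why a cell count suffices for CSF but not for ascites, when peritonitis is an expected event.

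There are also other safeguards: the stop for a 5-point rise in Maddrey's DF or MELD (5.4.2 item 3), discontinuation for adverse events and study medication stopped by the investigator's decision (5.4.2), emergency unblinding (6.6.2.1), SAE reporting within 2 working days and risk-based triggers (10.2.3), and "We will provide unblinded data on SAEs including infections and AKI to the DSMB on monthly basis". A reader might infer that a participant with culture-negative peritonitis has to stay on drug, or that nobody would notice. The documents do not support that. SAE reporting would pick up the cell count, and the investigator may stop drug. What is missing is an automatic hold. None of these routes mandates one for this finding, and Section 4.1 says that standard of care varies by region and institution.

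Finally, the benchmark itself has a doubtful unit. That is a fair reason to settle the unit first, but the omission remains whichever unit is right.

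**Conclusion.** The gap is real and should be closed. Culture-negative peritonitis triggers no mandatory hold unless SIRS plus a SOFA rise of at least 2 is present, and on that route restart may rest on negative cultures and an unchanged chest X-ray alone. The documents give no rate of culture-negative peritonitis, so no participant count can be offered.

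Two other inferences go too far. One is that only 3 doses are at issue; the rule that stops drug when there is no improvement makes 3 doses a limit neither on exposure without the hold nor on what an added hold can cost. The other is that the omission undermines the primary result; the logrank comparison of 90-day mortality is by ITT, and its method does not depend on the hold list.

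The conclusion rests on reading the hold lists as complete. It does not depend on the unit question.

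**What to change.** First confirm the unit of the ascitic thresholds in Section 10.2.2, and check the CSF unit there at the same time. Then add one line to the documented-infection list in both 5.4.1 and 6.6.1, alongside the culture entry: ascitic fluid white cell or neutrophil count above the 10.2.2 threshold, with or without positive cultures. The existing documented-infection restart rule then applies, so no separate restart clause is needed.

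This is one amendment and requires no new test, since an ascites tap is already among the sepsis studies done as indicated (Section 4.2, Data Collection). The downside is some additional 3-day holds, with permanent stopping after a first hold without improvement at 3 days or after a second hold. Their number cannot be estimated from the documents. If per mm³ was intended and the per-ml figures were copied unchecked, the trigger would be 1000 times too low and would cause needless holds.

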5.4.2 Reasons for Mandatory Trial Discontinuation

- 1. Persistent infection:** a) Participants with documented infection will be reassessed on 3rd day of the study drugs hold. If infection is responsive to antibiotics and participant is stabilized or improved, study drugs may be resumed at the discretion of the clinical care team. If there is no improvement after 3 days, study drugs will be stopped. b) For participants meeting only SOFA+SIRS criteria for stopping: if cultures of urine, blood, ascites, stool (including C. diff) are negative and CXR is unchanged, study drugs may be resumed at the discretion of the clinical care team. c) If the participant has a 2nd hold of study drugs due to infection/SOFA +SIRS criteria, study drugswill be stopped.
- 2. Pregnancy:** If a female participant becomes pregnant, she must stop taking study medication and must be withdrawn from the trial. The participant must be followed by the investigator through the end of her pregnancy. The mother (and infant) will be followed as considered appropriate by the investigator and the study designated physician ([name] or his designee). For reporting purposes, pregnancy is not considered a serious adverse event (SAE).
- 3. Clinical deterioration:** During the trial, if Maddrey's Discriminant Factor (DF) increases by 5 points and also exceeds 32, or MELD scores increases by 5 points and also exceeds 20, the study medication should be stopped, however the participant will remain in the trial, completing procedures as detailed in the Schedule of Procedures (Table 1). The study drugs will also be stopped if severe leukocytosis ($\geq 100,000/\text{mm}^3$) develops. Treating physicians may offer any other treatment that is considered as medically indicated and appropriate.
- 4. Suspected drug induced liver injury (DILI):** Hold the study drug if MELD increases by 5 from baseline or Child's score increases by 3 points from baseline plus >3 -fold increase in ALT from baseline on two consecutive occasions. These instances may represent either lack of therapeutic efficacy or DILI or some other etiology. If there is a competing etiology and DILI can be excluded, study drug can be resumed within 3-4 days. However, if DILI cannot be excluded, then the study drug will be permanently discontinued. Additional reasons for study drug discontinuation include unexplained elevation in ALT $> 5 \times$ baseline or $> 500 \text{ U/L}$ on two consecutive occasions or unexplained elevation in Alk P $> 3 \times$ baseline or $> 500 \text{ U/L}$ on two consecutive occasions. It should be noted that cholestatic DILI may have a devastating impact on participant survival in individuals with advanced liver disease.
- 5. Lille score:** Participants in either arm who have a Lille score of >0.45 on day 7 will stop bottle 1(prednisone/ placebo) and will continue with bottle 2 (zinc/zinc placebo.)

a) Other Reasons for Trial or Treatment Discontinuation

The following events are considered appropriate reasons for a participant to discontinue from the trial:

- The participant withdraws consent or requests to be withdrawn from the trial. It is fully understood that all participants volunteer for the trial and that they may withdraw their consent at anytime.
- The participant experiences an adverse event that in the opinion of the site investigator or the primary investigator of the trial (i.e., study designated physician, [name]) is caused by or exacerbated by any of the trial procedures or study medication, of sufficient intensity to warrant discontinuation.
- The participant refuses to comply with the requirements for trial participation.
- Termination of the trial due to DILI concerns: The Data Safety and Monitoring Board (DSMB) should carefully monitor the number of discontinuations due to MELD/Child's Score worsening in three treatment groups. Since this trial is not powered for rare adverse events, one should not look for statistically significant imbalance among treatment groups, but the DSMB should consider numerical imbalances that its members deem clinically significant. While it may be straight forward in some instances (for example, 2 discontinuations in groups A but 5 discontinuations in group B) but in other instances it may not be as clear cut and one may continue the trial for a growing trend. In any case, the DSMB is advisory in nature, and it makes a recommendation to the Sponsor, NIAAA. In addition to seeking the AlcHepNet Steering Committee input, the NIAAA may seek external input to assist in its deliberation if the DSMB recommends that the clinical trial must be terminated due to safety concerns.

When possible, the investigator should discuss the potential discontinuation of a participant with the study designated physician ([name] or his designee) in advance.

b) Participant Discontinuation Notification

The investigator must notify the study designated physician ([name] or his designee) as soon as possible if any participant prematurely discontinues from the trial. The date when the participant is withdrawn and the primary reason for discontinuation must be recorded in the CRF; additional information may be requested to complete a discontinuation narrative. Participants will be considered “lost to follow up” only after reasonable, documented attempts to reach the participant prove unsuccessful. In all cases, a reasonable effort must be made to determine the reason(s) that a participant fails to return for required trial visits or discontinues from the trial.

If a participant stays in the study but discontinues study medication (either by participant's choice, or by the investigator's decision), then study measurements should be performed according to the Schedule of Trial Procedures, Table 1 (rather than expediting study visits, or measurements). Patients will be followed until the final evolution (stability, worsening, or resolution) of the event that invoked drug discontinuation and followed until the end of the trial, if they are willing to do so.

